5.9.4. Procedure in case of emergency or pregnancy

If a serious or urgent situation arises, the sponsor and investigator are obliged to immediately take the urgent safety measures necessary to protect the research subjects. Examples of such measures may include discontinuing the clinical trial, temporarily or introducing additional monitoring measures. The sponsor shall notify the Swedish Medical Products Agency and the Ethical Review Authority as soon as possible of the urgent safety measures taken by the investigator or sponsor.

Any pregnancies among research subjects will be monitored until delivery. If the fetus/child has any form of congenital malformation, this will be reported as a serious adverse event (SAE).

There is limited experience with the use of Comirnaty in pregnant women. However, animal studies have not shown any direct or indirect harmful effects on embryo/fetal development, birth, or postnatal development, according to the summary of product characteristics.

5.9.5. Annual safety report (Development Safety Update Report, DSUR)

During the study, an annual safety report (DSUR) will be sent to the Swedish Medical Products Agency. The report contains a summary of the SAEs and SUSARs that have occurred, a summary assessment of the safety of the research subjects included in the study, and information on whether the benefit-risk assessment has changed since the study was approved.

5.9.6. Reference safety information

The reference safety information is described in the summary of product characteristics (SPC) for Comirnaty, sections 4.3, 4.4, and 4.8.

5.9.7. Discontinuation criteria

Participants may choose to withdraw from the study at any time without giving a reason. Specific grounds for **discontinuation of study treatment**

- The participant withdraws their consent
- Participants who do not meet the compliance requirements
- If SUSAR, SAE, severe AE, or other medical condition arises, where continued study participation could pose a risk to the participant, in the investigator's judgment, the study drug treatment will be discontinued. The participant will then be offered medical follow-up within the framework of the study.
- Participants who become pregnant during the study
- Severe/systemic allergic reaction to the vaccine.
- The patient has not completed follow-up (lost to follow-up).
- The investigator has the right to discontinue participation in the study if there are reasons that may affect the individual's safety.
- The relevant authority may terminate the study

If an individual withdraws, information collected during the time they were participating in the study will be used to perform the analyses described. A follow-up visit will be offered to individuals who have discontinued their participation.

No Data and Safety Monitoring Committee (DSMC) is planned to be established in this open-label, non-randomized study. This is because Comirnaty has already been studied in approximately 21,000 individuals regarding its safety profile. This is an open-label study, and we do not expect an increased number of AE/SAE/SUSAR in primary populations.

6. STATISTICS

6.1. Determination of the number of subjects

The primary purpose of this study is to study the immune response after the mRNA vaccine Comirnaty in a small study population (Phase IV study) in a descriptive or exploratory manner. The number of research subjects in the patient groups is based on the number of available patients who could be included at the respective clinics and the feasibility at a time when vaccination has already begun in Sweden. Several of these diseases/conditions are rare, with Karolinska University Hospital having the largest cohorts in Sweden, but with a limited number of patients available to participate in clinical trials.

The primary evaluation variable is the effect measured as the proportion of individuals who seroconvert in patients versus controls. For this, odds ratios and

analyzed using the Chi2 test where $\alpha=0.05$. With a patient group size of N=540, the power is >80% even with a conservatively estimated effect size of 0.15.

6.2. Analysis populations

Population	Description of population
Full analysis set population	All study participants who have received at least one dose of vaccine
Population with two doses of vaccine	All study participants who received two doses of vaccine and had a test result at 2 weeks after the second vaccine dose.
Population with evaluable reactogenicity after dose 1	All study participants who have received at least one dose of vaccine and have at least one measurement of reactogenicity after the first dose.
Population with Evaluable reactogenicity after dose 2	All study participants who have received two doses of vaccine, and had at least one measurement of reactogenicity after the second dose.

The number and percentage of study participants who are enrolled in the study, complete the study, and discontinue the study will be presented. Reasons for discontinuation will also be presented.

6.3. Planned analyses

6.3.1. Descriptive analyses

- The number and percentage (95% CI) of study participants with co-morbidity and other baseline characteristics.
- Previous and ongoing treatments will be summarized.
- Description of abnormal findings on complete or targeted physical examinations, vital parameters, clinical laboratory tests, and pregnancy tests.

6.3.2. Analyses of primary endpoint:

- Proportion (95% CI) receiving a positive SARS-CoV-2 IgG serology test result after two vaccine doses, three weeks after the second vaccine dose in the "population with two doses of vaccine," and having a negative SARS-CoV-2 serology test result at baseline, i.e., seroconverting.
- Chi² test is used for comparisons with the control group.

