5.2.4. Day 21 after first vaccine dose (+/-3 days, vaccine dose 2 given)

The following procedures will be performed at the study unit with study participants present. Sampling will be performed prior to vaccination.

Sampling group A

- Review of health declaration questions in Vaccinate, according to care routine before vaccination.
- Vital parameters: Blood pressure, pulse, temperature, and respiratory rate are measured. If the temperature is \geq 38 degrees, the study participant is rescheduled for vaccination on another day, when the person has been fever-free for at least 48 hours.
- Review of adverse events (AE/SAE/SUSAR).
- Review of concomitant medication (all new drugs, including immunosuppressive/immunoglobulin treatments).
- Sampling for SARS-CoV-2 IgG serology and more detailed analyses of humoral immunity (blood).
- Sampling for humoral immunity (saliva).
- Sampling of clinical laboratory tests including blood count (hemoglobin, white blood cells, and platelets) and differential count (neutrophils, lymphocytes, monocytes, basophils, and eosinophils), liver function (ALAT, ASAT, bilirubin, ALP), and creatinine.

- Sampling of HIV-RNA for HIV-infected individuals.
- Vaccine dose 2 is given (in case of anaphylaxis or other significant side effect likely to be related to Comirnaty, this dose will not be given).
- Study participants remain at the healthcare facility for at least 15 minutes (30 minutes for those with bleeding disorders) after vaccination.
- A diary is given to the study participant/information about the eDiary.

Sampling group B

All procedures are performed at the study unit:

- Review of health declaration questions in Vaccinate, according to care routine before vaccination.
- Vital parameters: Blood pressure, pulse, temperature, and respiratory rate are measured. If the temperature is \geq 38 degrees, the study participant is rescheduled for the vaccine dose injection on another day, when the person has been fever-free for at least 48 hours.
- Review of adverse events (AE/SAE/SUSAR).
- Review of concomitant medication (all new drugs, including immunosuppressive/immunoglobulin treatments).
- Sampling for SARS-CoV-2 IgG serology and more detailed analyses of humoral immunity (blood).
- Sampling for humoral immunity (saliva).

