- Sampling of clinical laboratory tests including blood count (hemoglobin, white blood cells, and platelets) and differential count (neutrophils, lymphocytes, monocytes, basophils, and eosinophils), liver function (ALAT, ASAT, bilirubin, ALP), and creatinine.
- Sampling of HIV-RNA for HIV-infected individuals.
- Sampling for analysis of cellular immunity (blood).
- Vaccine dose 2 is administered (in the event of anaphylaxis or other significant side effects likely to be related to Comirnaty, this dose will not be administered).
- Study participants remain at the healthcare facility for at least 15 minutes (30 minutes for people with bleeding disorders) after vaccination.
- A diary is given to the study participant/information about the eDiary.

5.2.5. 2-week follow-up (2-week FU) after the second vaccine dose (+/-3 days)

Sampling group A

All contact between study participants and study staff (research nurse or investigator) can be done remotely by phone (or chat, if the Always Open function is available). Can also be done on site, if it coincides with the study participant's regular visit to the study unit, or if the study participant prefers to be sampled at the study unit). Blood samples can be taken at any of the Karolinska University Laboratory's

sampling units in Stockholm, and saliva samples can be sent in a stamped envelope to Karolinska Institutet:

- Review of the diary (local and systemic reactogenicity).
- Review of adverse events (AE/SAE/SUSAR).
- Review of concomitant medication (all drugs from, including immunosuppressive/immunoglobulin treatments).
- Sampling for SARS-CoV-2 IgG serology and more detailed analyses of humoral immunity (blood).
- Sampling for humoral immunity (saliva).
- Sampling of clinical laboratory samples including blood count (hemoglobin, white blood cells, and platelets) and differential count (neutrophils, lymphocytes, monocytes, basophils, and eosinophils), liver function (ALAT, ASAT, bilirubin, ALP), and creatinine.
- Sampling of HIV-RNA for HIV-infected individuals.

Sampling group B

All procedures are performed at the study unit:

- Review of the diary (local and systemic reactogenicity).
- Review of adverse events (AE/SAE/SUSAR).
- Review of concomitant medication (all drugs from, including immunosuppressive/immunoglobulin treatments).
- Testing for SARS-CoV-2 IgG serology and more detailed analyses of humoral immunity (blood).
- Sampling for humoral immunity (saliva).

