¹ Includes blood count (hemoglobin, white blood cells, and platelets) and differential count (neutrophils, lymphocytes, monocytes, basophils, and eosinophils), liver function (ALT, AST, bilirubin, ALP), and creatinine.

IgG analysis in blood only at screening. If the screening visit is conducted via video contact, these samples will be taken on day 0, before the injection of the first vaccine dose.

² Samples will be taken before vaccination.

³ Blood samples can be submitted at Karolinska University Laboratory's sampling units in Stockholm, and study participants do not need to be at the study unit. Saliva samples can be sent by mail.

⁴ During screening visits, previous medications/treatments are noted in accordance with 5.5.2. All medications are noted during screening visits. During the period from the day of the vaccine dose until 14 days after, all medications are recorded after each vaccine dose. During other periods during the study, only new immunosuppressive/immunoglobulin treatments are noted, in accordance with 5.5.2.

⁵ Targeted examinations for symptoms during the study period, if necessary.

⁶ Blood pressure, pulse, temperature, and respiratory rate are measured.

⁷ Diary is issued on day 0/study participants receive an e-diary.

⁸ AE is monitored from the first and second vaccine doses until 14 days after each vaccine dose.

⁹ SAE/SUSAR is monitored within the period from the first vaccination day to 6 weeks after the second vaccine dose.

¹⁰ Nasopharynx sample on day 0 and, if necessary, in case of COVID-19 symptoms. COVID-19 symptoms are: cough, fever \geq 38 degrees, breathing difficulties, runny nose, nasal congestion, sore throat, headache, nausea, muscle and joint pain, impaired sense of smell and taste, or diarrhea.

¹¹ If the screening visit takes place via video contact, a pregnancy test will be performed on day 0, before the first vaccine dose is administered.

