5.5.7. Clinical laboratory tests

The predefined safety samples according to 5.2 will be taken and recorded. Any abnormal sample value that is considered clinically significant by the investigator should be recorded as an AE, unless it is due to an existing medical condition or is due to treatment given for the existing medical condition.

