5.7. Definitions of adverse events

5.7.1. Incident/Adverse event (AE)

Any incident (AE), or worsening of an existing medical condition in a research subject who has received an investigational drug, regardless of whether it is causally related to the treatment or not, i.e., it may be an adverse and undesirable sign (including an abnormal laboratory finding), symptom, or disease that is temporally associated with the use of an investigational medicinal product, regardless of whether it is related to the investigational medicinal product or not.

However, events that are an expected consequence of the underlying disease, such as worsening of the underlying disease, will not be reported as an AE. This is because we do not expect Comirnaty to affect the progression of the underlying disease.

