6.3.3. Analyses of secondary endpoints

- Proportion (95% CI) seroconverting to a positive response to SARS-CoV-2 IgG serology after two doses of vaccine, at 3 months and 6 months after the second vaccine dose, measured in the "two-dose vaccine population" compared with the control group.
- Proportion (95% CI) experiencing adverse events, with AE/SAE/SUSAR. Number and proportion (95% CI) experiencing local reactions and systemic reactions are measured in the "Full analysis set population".
- Proportion (95% CI) receiving a new diagnosis of SARS-CoV-2 infection through a positive PCR test is measured in the "Full analysis set population."

- Comparisons are made with the control group.

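### Safety laboratory tests are taken before dose 1 and twice afterwards, but section 6.3.1 plans no comparison with each person's pre-dose value, so worsening in patients already abnormal at baseline need not be shown

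*Combined protocol and SAP*

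**What the plan says.** **Collection.** The same panel is scheduled three times in both sampling groups.

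- Before dose 1, at screening or on day 0. Footnote 1 of Table 2 states: "If the screening visit is conducted via video contact, these samples will be taken on day 0, before the injection of the first vaccine dose".
- At day 21, before dose 2 (5.2.4): "Sampling of clinical laboratory tests including blood count (hemoglobin, white blood cells, and platelets) and differential count", with liver function and creatinine.
- Two weeks after dose 2 (5.2.5): "Sampling of clinical laboratory samples including blood count (hemoglobin, white blood cells, and platelets) and differential count", again with liver function and creatinine.

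**Analysis.** Section 6.3.1 lists "Description of abnormal findings on complete or targeted physical examinations, vital parameters, clinical laboratory tests, and pregnancy tests". Abnormal is not defined. Sections 6.3 and 6.4 give no change from baseline, shift table, grade or by-visit display for these tests.

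**AE route.** Section 5.5.7 states: "Any abnormal sample value that is considered clinically significant by the investigator should be recorded as an AE". It then adds the exception "unless it is due to an existing medical condition or is due to treatment given for the existing medical condition". Section 5.7.1 says that "events that are an expected consequence of the underlying disease, such as worsening of the underlying disease, will not be reported as an AE", and 5.9.1 repeats that exemption. Section 6.3.3 summarises AEs as "Proportion (95% CI) experiencing adverse events, with AE/SAE/SUSAR".

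**The concern.** The stated laboratory summary is keyed to whether a finding is abnormal. That can work where almost everyone starts within the reference range. It works poorly where a patient may already be outside the range because of the disease or its treatment, since the label then need not change when the value does.

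The protocol anticipates such patients. Section 5.3.1 makes provision for participants with thrombocytopenia, and 5.9.1 expects frequent non-serious medical events from the existing condition in most of the primary population.

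Safety and tolerability is a secondary objective. Physical examination is symptom-driven only (5.3.2), and no data and safety monitoring committee is planned (5.9.7). The blood panel is thus scheduled, objective safety information on all participants. Each person has a pre-dose value to compare with, and the plan does not ask for that comparison.

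**Working it through.** The plan states no figure on this point, so the check sets its sections side by side.

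1. **Is there a baseline?** Yes. Section 5.2.2 and footnote 1 of Table 2 place the first panel before dose 1 in every case. The day-21 sample then follows one dose, and the 2-week sample follows two.

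2. **Does any analysis section use it?** No.
   - 6.3.1 names the laboratory tests but only asks for abnormal findings to be described.
   - 6.3.3 covers serology, AEs, reactogenicity and PCR-confirmed infection.
   - 6.3.4 plans a change from study start for HIV DNA. The plan therefore specifies within-person change where it wants it, but not for the safety panel.
   - 6.4 gives mean and SD, or median and IQR, for continuous variables. It names neither laboratory tests, visits nor change.

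3. **What can a status description miss?** Take two patients whose value before dose 1 is c, above the upper reference limit. One stays at c. The other rises to kc, with k > 1. Both are abnormal at all three samples. Only the ratio to baseline (1 against k) separates them.

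4. **Does the AE route catch the second patient?** Only if two conditions both hold.
   - The investigator judges the value clinically significant (5.5.7).
   - The investigator does not attribute it to the existing condition or its treatment (5.5.7), or regard it as expected worsening of the underlying disease (5.7.1, 5.9.1).

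   A further rise in a value that the disease or its treatment had already made abnormal is the case most easily attributed to that cause, and attribution here is open-label.

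5. **Can the gap be sized?** Suppose a share b of a group is outside the range before dose 1, and a share w worsens irrespective of baseline status. A count of abnormal patients can then rise by at most w × (1 − b). The part that cannot appear is w × b, and as a share of all worsening this is (w × b) / w = b. The result only returns the assumed b. The documents give neither b nor w, so no figure follows from them.

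**The case against.** The case on the other side has force in five places.

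- **A reader might infer that such worsening is reported nowhere.** The documents do not support that. The exception in 5.5.7 turns on cause, not on baseline status. A clinically significant rise not attributed to the condition or its treatment is an AE even in a patient already out of range, and counts in the 6.3.3 proportion. The AE definition in 5.7.1 also includes abnormal laboratory findings and worsening of an existing condition, subject to its exemption.
- **A description need not be a normal/abnormal count.** Section 6.3.1 fixes no such count, and the rule in 6.4 could be stretched to cover these tests. This stands, so the point is that the plan does not require worsening to be shown. Separate group means or medians at each visit would still not be paired within persons.
- **A reader might want to put a figure on the hidden share.** With w = 10% and b = 30%, 60% or 90%, all assumed, the visible rise is at most 7, 4 or 1 percentage points. The hidden share of 30%, 60% or 90% is then simply b. It also depends on reading 6.3.1 as a count, so it is not evidence about this trial.
- **A reader might treat creatinine and liver tests as the trial's signal of graft harm.** No section gives them that role. Biopsy-verified rejection and graft-versus-host disease are separate exploratory endpoints (4.2), and routine clinical follow-up continues (5.3.2).
- **Paired change will not separate vaccine from disease.** There is no unvaccinated comparator, and immunosuppressive treatment may change. This stands and limits how the new tables may be read.

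It is also true that laboratory change is not a listed endpoint, that 6.1 calls the study descriptive or exploratory, and that 2.1 already reports seroconversion results from 2 weeks after dose 2. These lower the weight. They do not make the status-based description the better summary of paired data.

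**Conclusion.** The point holds as a gap in a descriptive safety analysis. A pre-dose panel and two later panels are collected, the only named summary is keyed to abnormality, and the AE exemptions leave out worsening attributed to the existing condition or its treatment. The plan therefore does not require worsening to be shown in patients already abnormal at baseline.

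Its size cannot be stated. The conclusion assumes only that some patients are outside the reference range before dose 1, which the provisions in 5.3.1 and 5.9.1 make reasonable. The change is worth making for the secondary safety objective. Seroconversion and its comparison with controls are not affected.

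**What to change.** In 6.3.1, keep the existing line and add for the laboratory tests, by patient group and controls:

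- The paired change from the pre-dose-1 value to day 21 and to 2 weeks after dose 2, as median and IQR, with the ratio to baseline for creatinine and liver tests.
- A shift table of baseline against worst post-dose category, using the laboratory's reference ranges (below, within, above) or a grading scale named in advance. State how the worst category is chosen for tests that can move either way.

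The paired change is the essential part. A three-category shift table alone cannot separate stable from worse among patients who start and stay on the same side of the range.

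State that the tables are descriptive, without tests and without attributing change to the vaccine, and that they were specified after the 2-week results were known. The AE recording rules need not change for this.

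**Cost.** The panel has 13 tests (3 blood count, 5 differential, 4 liver, 1 creatinine). With 2 post-dose samples and 6 groups this gives 13 × 2 × 6 = 156 paired summaries, which fit in a few tables. The protocol's existing scales cover only local and systemic reactions (5.8.3), so the laboratory category rule has to be named. No new samples or visits are needed.
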